#### 10.2 Proposed Analysis

All statistical analyses will be governed by a comprehensive Statistical Analysis Plan, which will be authored by the study statistician and approved by the Trial Steering Committee and the Data Monitoring Committee before the main study outcome data are examined. All analyses will be carried out using Stata. In accordance with CONSORT guidelines, we will report all participant flow. Descriptive statistics of recruitment, drop-out and completeness of interventions will be provided.

Effectiveness Analysis: The main effectiveness analysis will be via intention-to-treat including all participants, with no planned interim analysis for early termination for either overwhelming evidence of effectiveness or abandoning for futility. Baseline characteristics will be presented by randomised group without formal statistical tests. We will test the primary hypothesis for between-group change in the primary outcome for each of the two pre-specified comparisons (CBA + usual care vs usual care alone and PEP + usual care vs usual care alone) using repeated measures mixed model, with subject as a random effect, and a suitably specified covariance structure (e.g. Autoregressive [1] (AR[1]), rheumatology healthcare professional as a random effect (to adjust for any clustering by rheumatology healthcare professional), with baseline outcome measure, and any other strongly predictive baseline measures, including the minimisation factors of presence/absence of depression and centre, and diagnosis. Treatment and its interaction with time will be fitted as fixed effects, and we apply standard regression diagnostics. The analysis will use statistical techniques for handling missing outcome data using multiple imputation under a missing at random (MAR) assumption. The secondary outcomes will be analysed using an analogous method. The main estimate of treatment effect will focus on the 56 weeks after baseline.

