11.2 Statistical Analysis

LIFT has repeated measures on individual participants nested within site suggesting a multilevel model with an appropriate link function depending on the outcome. The analysis will adjust for the outcome variable at baseline as a covariate (when available) as well as the design factors also at baseline [diagnosis (RA, SLE, AxSpA or other IRD), the presence/absence of depressive symptoms HADS depression subscale >10)]. Centre clustering will be accounted for using a random effects robust variance.

11.2.1 Primary Outcome - Effectiveness Analysis.

We will test the primary hypothesis for between-group change in the primary outcome for each of the two pre-specified comparisons (CBA + usual care vs usual care alone and PEP + usual care vs usual care alone) using treatment and its interaction with time fitted as fixed effects, and we apply standard regression diagnostics. The main analysis will focus on the 56 weeks after baseline – providing effect sizes for each of the active arms compared to usual care. Standard regression diagnostics will be applied.

A Complier Average Causal Effect (CACE) analysis will be considered as a sensitivity analysis. Patent engagement & adherence (therapist view) at 8 weeks forms the CACE variable (if missing the 4 weeks reported value will be substituted) as a continuous instrumental variable in the CACE analysis

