11.4 Quantitative evaluation Analysis

The main analysis to assess preference on the treatment effect whereby 'no preference' will be considered as being 'not matched' i.e. did not get their preferred treatment.

Two sensitivity analyses will be considered regarding those who 'had no preference'.

- To drop them from the analysis
- To include in the 'matched' group.

Another set of sensitivity analyses will assess the impact of adjusting for 'how positive' participants were about receiving their preferred option, summarised in the table see dummy tables below*. *post randomisation moderator effects such as therapist/HCP effect analyses, patient adherence will be a secondary analysis phase.*

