11.5 Missing Outcome Data

The sensitivities of treatment effect estimate to missing outcome data will be explored; these models will explore the robustness of the treatment estimate to whatever small amount of missing data there is. We will follow the strategy outlined in White *et al* (2). The analysis will use all available data that we believe are valid under the assumption of missing at random. The multilevel models used to account for follow-up over time will also internally impute any covariate missingness assuming they are MAR. However, the models only require the outcome variable at baseline as a covariate (when available) as well as the design factors also at baseline and so may be imputed as described above if missingness is substantial. In a trial this is unlikely. Our final estimates at each follow-up will be only for the actual numbers obtained for each of the Outcomes for the primary ITT analyses. If required, that is if the missingness for the primary outcome is >10%, sensitivity analyses will include multiple imputation such as MICE and/or we will explore a range of values for missing data imputed under missing not at random assumptions (such as pattern mixture models); the extent of

missingness will be assessed along with a determination of if the data are MAR or MCAR. In addition, a comparison of baseline characteristics of the responders and non-responders will be conducted with respect to the primary outcome.

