13.4 Primary outcome summaries and model Estimates

Table 8: Primary outcome for Fatigue: Summaries*# and Model results

	CBA N =	PEP N=	Usual Care N =	Effect sizeª	95% CI	p- value	Effect size ^b	95% CI	p- value
Chalder Fatigue	Scale (Con	bined Liker	t score) 0-33 *c						
Baseline									
10wks									
28wks									
56wks (p)									
Fatigue Severity	/ Scale (FSS) *c							
Baseline									
10wks									
28wks									
56wks (^p)									
Baseline									
10wks									
28wks									
56wks (p)									

All models adjusted for their baseline outcome measure, HADS depression subscale >10 at baseline as fixed effects fixed effect with Centre clustering and individuals nested within centres as random effects *Continuous data:n; mean (sd), median (IQR) and (min, max)

Binary x/n (%)

^aMean difference between CBA and Usual care

^b Mean difference between PEP and Usual care

P Primary time point

^cMultilevel mixed-effects generalized linear model (glm) accounting for different time points.

Recall:

- The primary intention to treat analyses will compare PEP + usual care versus usual care alone, and CBA + usual care versus usual care giving effect sizes ^a and ^b
- The main estimate of treatment effect will focus on the 56 weeks after baseline.

- If the effect of intervention is positive on the CF, then the FSS outcome will be formally analysed. Should the intervention have no effect on the CF, then an explorative analysis of the FSS outcome will be performed.
- All analyses and reporting will follow the guidelines of the CONSORT statement developed specifically for social and psychological intervention trials ³
- CACE analysis as a sensitivity analysis will be considered for the primary outcome Chalder Fatigue

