13.5 Secondary outcome summaries and model Estimates

Table 9: Summaries*# and Model results

	CBA N =	PEP N=	Usual Care N =	Effect sizeª	95% CI	p- value	Effect size ^b	95% CI	p- value
BRAF-MDQ (fati	gue) *c								
Baseline									
10wks									
28wks									
56wks (p)									
HADS *c									
Anxiety									
Baseline									
10wks									
28wks									
56wks (^p)									
Depression									
Baseline									
10wks									
28wks									
56wks (^p)									
Short Form-12 *	2								
SF-12 PCS									
Baseline									
10wks									
28wks									
56wks (^p)									
SF-12 MCS									
Baseline									
10wks									
28wks									
56wks (p)									
Pain numerical r	ating scale	*c							
Baseline									
10wks									
28wks									
56wks (p)									
Sleep problem so	ale *c								
Baseline									
10wks									
28wks									

SAP version 1: LIFT

56wks (p)									
WPAI*c for all 4 domains									
Baseline									
10wks									
28wks									
56wks (p)									
Valued Life Activ	vities Scale	(short 14 iter	ms) *c						
Baseline									
10wks									
28wks									
56wks (p)									
Global Outcome	e								
10wks									
28wks									
56wks (^p)									

All models adjusted for their baseline outcome measure where appropriate (not Global outcome), HADS depression subscale >10 at baseline as fixed effects fixed effect with Centre clustering and individuals nested within centres as random effects

*Treated as Continuous data: n; mean (sd), median (IQR) and (min, max)

Binary x/n (%)

^a Mean difference between CBA and Usual care

 $^{\rm b}$ Mean difference between PEP $\,$ and Usual care

^cMultilevel mixed-effects generalized linear model (glm) accounting for different time points.

^e Multilevel mixed-effects glm ordinal regression and robust variance – (ref Zou 21004 (5), accounting for time points as interaction terms

^p Primary time point

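### The SAP drops the therapist random effect that the protocol puts in the primary model, so both primary contrasts' standard errors may be too small

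*SAP*

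**What the plan says.** Protocol 10.2 specifies the primary repeated-measures mixed model with "rheumatology healthcare professional as a random effect (to adjust for any clustering by rheumatology healthcare professional". The purpose is stated with the term.

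The SAP has no therapist level in the primary analysis. Section 11.2 describes repeated measures on participants within sites and adds that "Centre clustering will be accounted for using a random effects robust variance". The Table 8 footnote (primary outcomes) gives "fixed effect with Centre clustering and individuals nested within centres as random effects"; the Table 9 footnote (secondary outcomes) likewise gives "Centre clustering and individuals nested within centres as random effects".

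Therapists appear in SAP 11.4, which says that "post randomisation moderator effects such as therapist/HCP effect analyses, patient adherence will be a secondary analysis phase".

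The sensitivity analyses that the SAP names are:
- adherence (11.2.1): "A Complier Average Causal Effect (CACE) analysis will be considered as a sensitivity analysis"
- missing outcomes (11.5): "sensitivity analyses will include multiple imputation such as MICE"
- the handling of patient preference (11.4).

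On precedence, protocol 10.2 says "All statistical analyses will be governed by a comprehensive Statistical Analysis Plan".

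**The concern.** The protocol made a deliberate choice about clustering, and the SAP reverses it without explanation. Because the SAP governs, the model without the therapist term is the one that will be run.

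CBA and PEP are given one-to-one by therapists, and usual care has none (protocol 4.3). If patients of the same therapist have correlated outcomes, the variance of the active-arm mean rises on one side of each primary contrast. A model without that level does not see the extra variance. Standard errors and p-values are then too small, and the risk of a false positive exceeds the nominal level. Studying therapist effects later as moderators answers a different question and leaves the primary standard errors as they were.

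Whether centre terms pick up the therapist correlation depends on two things that the documents leave open:
- **Nested or crossed.** Protocol 1.2 (delivery by the rheumatology team), 4.3.2 (a face-to-face first PEP session) and Appendix 3 (therapists at all sites) suggest that therapists sit within centres. The protocol Summary describes central, remote delivery, which would let them cross centres.
- **Variance estimator.** The phrase in SAP 11.2 could mean model-based random effects or a sandwich variance clustered on centre.

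**Working it through.** **The plan's own figure.** Inputs from protocol 10.1 and SAP 10: difference 2, SD 4, 2.5% per comparison (taken as two-sided), power 90%.

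n = 2 × 4² × (2.241 + 1.282)² / 2² = 99.3, so 100 per arm (power at 100 is 90.2%). With 20% dropout, 100/0.8 = 125. The figure reproduces and contains no allowance for clustering.

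**Closed form, therapist correlation not absorbed by centre.** Assumed, because the documents give neither: 5 to 20 therapists per active arm and ICC 0.01 to 0.05. With m = 100 / (therapists per arm):

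- Var(difference) = (16/100)[1 + (m − 1)ICC] + 16/100
- inflation F = Var / 0.32
- SE shortfall = 1 − 1/√F
- actual error = 2[1 − Φ(2.241/√F)]
- power = Φ(2/SE − 2.241), with SE = √Var

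| Therapists per arm, ICC | F | SE too small by | Error at nominal 2.5% | Power |
|---|---|---|---|---|
| 20, 0.01 | 1.020 | 1.0% | 2.65% | 89.6% |
| 10, 0.02 | 1.090 | 4.2% | 3.18% | 87.4% |
| 5, 0.05 | 1.475 | 17.7% | 6.50% | 74.8% |

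For the middle row, m = 10 and Var = 0.16 × 1.18 + 0.16 = 0.3488.

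At the two-sided 5% level given in SAP 11.1, the error runs from 5.2% to 10.7%. An assumed baseline correlation of 0.5 multiplies the variance by 0.75. With the ICC on that adjusted scale, power is 96.4%, 95.2% and 86.9% (97% without clustering). If the therapist variance instead stays at its unadjusted value, error is 2.70%, 3.42% and 7.95%, and power 96.3%, 94.7% and 83.0%.

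**Null simulation, model-based SE with a centre random intercept.** 4,000 trials per setting, both contrasts counted; Monte Carlo SE about 0.2 points at 2.5%. Assumed: 100 per arm, SD 4, baseline correlation 0.5, centre ICC 0.02, therapist variance = ICC × 16, complete 56-week outcome only, normal reference. Settings: crossed (10 centres; 5, 10 or 20 therapists per arm) and nested (5 or 10 centres, one CBA and one PEP therapist each). Rejection at nominal 2.5%:

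| ICC | Therapist term omitted | Therapist term added |
|---|---|---|
| 0 | 2.4%–2.7% | 2.0%–2.4% |
| 0.02 | 2.8%–5.0% | 2.4%–3.3% |
| 0.05 | 3.5%–8.3% | 2.7%–4.0% |

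At ICC 0.05, mean SE over true SE is 0.77–0.94 with the term omitted and 0.98–1.00 with it added. The top end exceeds the first closed-form table because therapist variance is held on the unadjusted scale here; the matching closed-form figure is the 7.95% above.

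**Same simulation, sandwich clustered on centre, therapist term omitted.**
- Nested: rejection at ICC 0, 0.02 and 0.05 is 9.4%, 9.1%, 9.0% with 5 centres and 5.2%, 5.4%, 5.8% with 10. Root-mean-square SE over true SE is 0.98–1.00. Omission changes little; the excess comes from a normal reference with few centres, and a t reference (centres − 1 df) gives 2.5%–2.7%.
- Crossed, 10 centres, t reference: 2.6%–2.8% at ICC 0, 2.6%–4.0% at 0.02, 3.2%–6.7% at 0.05.

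**Second simulation, different set-up** (2,000 runs, centre as fixed effects, no baseline covariate, 6 centres, 6 therapists, ICC 0.05; SE in SD units):

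| Therapists | True | Model-based | Centre sandwich |
|---|---|---|---|
| Nested | 0.169 | 0.139 | 0.167 |
| Crossed | 0.164 | 0.140 | 0.140 |

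Only nesting combined with a centre sandwich removes the understatement.

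**The case against.** The strongest reply is that the harmless reading may be the right one. SAP 11.2 ties centre to a robust variance, which is compatible with random intercepts plus a centre sandwich. The face-to-face first session makes crossing hard to sustain, at least for PEP. The four combinations of design and estimator should therefore not be treated as equally likely. This stands as a limit on the claim: the textual discrepancy is certain, but its effect on the standard errors is conditional. It does not remove the point. The SAP states neither condition, and the harmless reading needs a small-sample reference when centres are few, which the SAP does not mention.

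The size rests wholly on assumed inputs, the simulation leaves out the 10- and 28-week visits and the diagnosis and depression terms, and the middle case is modest. All of that is true.

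The therapist term with a normal reference does not fully restore 2.5%: up to 4.0% remains at ICC 0.05. That also stands, but it is well below the 8.3% reached without the term.

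SAP 12 says the protocol will be consulted, and SAP 11.4 shows that therapist effects were considered. Neither puts the term back into the specified primary model.

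**Conclusion.** The concern holds. The SAP's primary model lacks a term that the protocol specifies for a stated reason. The SAP gives no justification, and no sensitivity analysis covers therapist clustering (centre clustering is covered).

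With a therapist ICC above zero and more than one patient per therapist, both primary contrasts have standard errors that are too small under model-based estimation, or under a centre sandwich if therapists cross centres. With nested therapists and a centre sandwich, the standard errors are about right.

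The documents do not fix the size. It ranges from negligible (many therapists, ICC 0.01) to more than double the nominal error (5 therapists per arm, ICC 0.05). This should be fixed before unblinding, because a clustering adjustment chosen afterwards would be open to challenge.

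**What to change.** Restore the therapist random effect in SAP 11.2 and 11.2.1 and in the Table 8 and 9 footnotes, and keep centre. Usual care has no therapist, so apply the effect in the CBA and PEP arms only and treat usual-care participants as singletons; the protocol does not spell this out. At minimum, justify the removal and pre-specify that model as a sensitivity analysis of the primary outcome before unblinding.

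Also state which estimator the variance phrase in SAP 11.2 means and whether therapists are nested in centres. Separately, if a centre sandwich with few centres is used, name a small-sample reference distribution; the omitted therapist term does not cause that error.

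The cost is SAP wording and one model term. Each active-arm participant has an allocated therapist (protocol 6.1), and session sampling already uses therapist identity (4.3.4). If the true ICC is zero, standard errors are about 2%–5% wider and the test is mildly conservative (2.0%–2.4% at nominal 2.5%). Therapist codes exist only in the active arms and could reveal allocation, so write the term now and fit it once the statistician's blinding has ended (SAP 4).

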# 4 STUDY DESIGN

The LIFT study is a multi-centre, three-arm randomised controlled trial testing usual care alone versus usual care with additional adapted CBA or PEP therapies (see 4.3).

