# 6 RANDOMISATION AND BLINDING

## 6.1 Randomisation Details

After the patient has provided written consent to participate in the study and eligibility has been confirmed, the member of the local research team will randomise the participant via the Clinical Trials Unit (CTU). The CTU is the Centre for Healthcare Randomised Trials (CHaRT) based within the University of Aberdeen. The CTU provides a 24 h randomisation web based service. Using a computer generated sequence, participants will be allocated to receive either of the two treatments or usual care (1:1:1 ratio). Randomisation will be minimised by diagnosis (RA, SLE, AxSpA or other IRD) and the presence/absence of depressive symptoms (Hospital Anxiety & Depression Scale (HADS) depression subscale >10) and will include a random element set at 20%. That is, 20% of all the allocated randomisations will be randomly re-allocated 50:50 to the remaining two treatment options.

Randomised participants will be contacted by the study co-ordinator (or designated deputy if unavailable) by post, email and/or telephone with information about their intervention and details of their allocated therapist, if applicable. All personal contact details will be only accessible in the password protected study database (see 8.2).

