11.8 COVID-19

The effect of COVD-19 will be explored. In the first instance, periods before, during and after COVID-19 will be summarised using appropriate descriptive statistics and graphical summaries. If need be, formal analysis will be carried out to explore the effect of COVID-19, that may include time of recruitment in relation to UK lock-down (23rd March 2020) and local conditions at the time each outcome is measured. Attempts will be made to account/adjust for the multiple lockdowns and variations of that around the country using emerging methodologies.

12 Technical Details

Protocol version (vs 11) will be consulted for this SAP. All statistical analyses will use stata (vs 15 for DMC's – and vs 16 for the final analyses). All results will be processed directly into PDF/Word from Stata via LaTEX (MiKTeX 2.9 at time of writing) for the DMC's, the use of putdocx commands in Stata 16 for the final Statistical Report.

13 Dummy Tables

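### SAP 11.2 names a robust variance for centre but not its level, reference distribution or number of centres; as a centre-clustered sandwich with z tests it would inflate the primary type I error

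*SAP*

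**What the plan says.** SAP 11.2 plans a multilevel model for repeated measures on participants within sites, adjusted for the baseline outcome, diagnosis and depressive symptoms. It then says "Centre clustering will be accounted for using a random effects robust variance". It gives no cluster level, small-sample correction or reference distribution. SAP 11.2.1 builds the two primary comparisons on this model, and SAP 11.2.2 carries the approach to the secondary outcomes.

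The dummy tables read differently. The Table 8 footnote (SAP 13.4) describes the primary model "with Centre clustering and individuals nested within centres as random effects" and does not mention a robust variance. In Table 9 (SAP 13.5) a robust variance is attached only to the Global outcome: "Multilevel mixed-effects glm ordinal regression and robust variance". Table 11 (SAP 13.7) attaches one to a modified Poisson model for treatment preference.

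Protocol 10.2 plans a mixed model with random effects for subject and for healthcare professional, lists centre among the baseline adjustment variables, and names no robust variance.

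On the number of centres, Protocol 4 says only "The LIFT study is a multi-centre, three-arm randomised controlled trial". SAP 12 names Stata ("vs 16 for the final analyses") but no estimation command. Protocol 6.1 randomises individual participants 1:1:1. SAP 10 sets each primary comparison at 2.5% so that the overall level stays within 5%.

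**The concern.** A robust (sandwich) variance clustered on centre estimates uncertainty from the scatter between centres. Its information is therefore limited by the number of centres, G, and not by the 375 participants. With few centres the standard error is noisy and, on average, too small for a normal reference. A z test then rejects too often.

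Participants are randomised individually, so a shared centre intercept largely cancels from the arm contrasts. A centre-clustered variance is not needed to deal with that intercept, yet it can damage the test.

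What is at stake is the p-value and interval for both primary comparisons at 56 weeks, the same quantities for the secondary outcomes, and the overall 5% level. SAP 11.2 and Table 8 also allow two different sets of standard errors from the same data, a choice that should be closed before the data are analysed.

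**Working it through.** **Inputs from the documents.** Difference 2 and SD 4 on the Chalder scale, 2.5% per comparison, 90% power (SAP 10; Protocol 10.1); 20% dropout (Protocol 5.1); three follow-up visits; 1:1:1 individual allocation.

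**Inputs not in the documents (assumptions).** Number of centres G, taken over 4 to 30; clustering of the robust variance on centre; z reference.

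**Step 1: the plan's own figure.** n per arm = 2(z₀.₉₈₇₅ + z₀.₉₀)² × SD²/difference² = 2(2.241 + 1.282)² × 16/4 = 99.3, rounded up to 100. Then 100/0.80 = 125 per arm and 3 × 125 = 375 in total. The sample size reproduces and is not in dispute. It presumes that each comparison really runs at 2.5%.

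**Step 2: approximation.** With the usual G/(G−1) factor, a centre-clustered statistic for a single contrast behaves roughly as t on G−1 degrees of freedom. Referred to z, its true error is 2 × P(t with G−1 df > z critical), where the critical value is 1.960 at 5% and 2.241 at 2.5%.

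| Centres | True error, nominal 5% | True error, nominal 2.5% |
|---|---|---|
| 4 | 14.5% (×2.9) | 11.1% (×4.4) |
| 6 | 10.7% (×2.1) | 7.5% (×3.0) |
| 8 | 9.1% (×1.8) | 6.0% (×2.4) |
| 10 | 8.2% (×1.6) | 5.2% (×2.1) |
| 15 | 7.0% (×1.4) | 4.2% (×1.7) |
| 20 | 6.5% (×1.3) | 3.7% (×1.5) |
| 30 | 6.0% (×1.2) | 3.3% (×1.3) |

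**Step 3: simulation under no treatment effect.** 300 evaluable participants, three arms, three visits, arm by visit, baseline and depression covariates. Assumed variance shares were centre 5%, participant 50% and residual 45%, with variance components treated as known, simple allocation and no variation of the treatment effect between centres. There were 2,000 trials (4,000 tests) per setting, with equal centre sizes or sizes spread over about 1:4. The Monte Carlo standard error at 2.5% is about √(0.025 × 0.975/4000) = 0.25 percentage points. The last column is the chance of at least one false positive when each comparison is tested at 2.5%.

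| Centres | Sandwich with z, nominal 2.5% (equal / unequal) | Model-based, nominal 2.5% (equal / unequal) | At least one false positive, sandwich with z (equal / unequal) |
|---|---|---|---|
| 4 | 11.3% / 12.9% | 2.5% / 2.1% | 20% / 23% |
| 6 | 7.9% / 8.3% | 2.3% / 2.6% | 14% / 15% |
| 10 | 5.1% / 5.2% | 2.3% / 2.2% | 9% / 10% |
| 20 | 3.9% / 4.2% | 2.7% / 2.5% | 7% / 8% |
| 30 | 3.6% / 3.6% | 2.6% / 2.6% | 7% / 7% |

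The simulation agrees with Step 2, and unequal centres are somewhat worse when centres are few. Over 4 to 30 centres, model-based errors gave 4.7% to 5.6% at nominal 5% and 2.1% to 2.9% at nominal 2.5%. A second simulation (375 participants, 20% loss by week 56, centre intraclass correlation 0.02) gave the same pattern: about 11% with 4 centres and 5% with 10 at nominal 2.5%, against 2.4% to 2.9% for model-based or participant-clustered errors.

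**Step 4: the same sandwich referred to t with G−1 df.** Simulated error returns to 4.9% to 6.2% at nominal 5% and 2.4% to 3.2% at nominal 2.5%. The price is a larger critical value. At nominal 2.5% it is 3.163 in place of 2.241 with 6 centres (ratio 1.41) and 2.433 with 20 centres (ratio 1.09).

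**The case against.** The strongest reply is that the SAP may never have intended a centre-clustered sandwich. The phrase in 11.2 can mean centre random effects, a sandwich, or both. Table 8 sets out the primary model with random effects only, and the dummy tables name a robust variance where one is wanted. On that reading the error is close to nominal. This stands as a possible reading, but it does not settle the matter: 11.2 is the methods text, it sits directly above the primary analysis, and a plain random-effects model would not need the word robust.

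It also stands that the number of centres and the z reference are assumptions, and that the reference distribution decides most of the harm (Step 4).

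Four stronger readings are tempting and should not be drawn:

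- *That each primary comparison will run at two to four times its nominal level.* That multiple fits about 5 to 10 centres at 2.5% and about 3 to 6 at 5%. The documents give no centre count.
- *That having fewer centres than coefficients is what makes the p-values too small.* The model has 14 fixed coefficients (intercept, 2 arm, 2 visit, 4 arm by visit, baseline, depression, 3 diagnosis). A rank-deficient matrix limits joint tests. Each primary comparison is a single contrast, and its inflation comes from the few degrees of freedom.
- *That every interval would be too narrow.* With 6 centres the robust standard error ranged from about 0.5 to 1.5 times the correct one (5th to 95th percentile). The optimism is an average property, and one trial's interval could be too wide.
- *That centre-level inference can never matter under individual randomisation.* This holds if the treatment effect does not vary between centres. The Step 3 simulation assumed so.

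**Conclusion.** The point holds in conditional form. SAP 11.2 and the Table 8 footnote do not define one set of primary standard errors, and no small-sample protection is written in. If the 11.2 sentence is carried out as a centre-clustered sandwich with z tests, the error exceeds nominal at every centre count examined from 4 to 30, and the overall 5% level is missed even at 30 centres (about 7% simulated). The excess is large with few centres and modest with 20 or more. If centre and participant random effects with model-based errors are what is meant, there is no material inflation.

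The size rests on the assumed range of centres, the z reference, clustering at centre level and the simulation settings in Step 3. SAP 11.1 quotes 5% for treatment effects where SAP 10 uses 2.5%. That is a separate matter, and it only changes which column of the Step 2 table applies. The point should be settled before the primary analysis because it governs both primary p-values and is cheap to close.

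**What to change.** State the number of centres in the SAP, make 11.2 and the table footnotes agree, and split the rule by type of outcome.

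- **Continuous outcomes (Table 8 and the continuous rows of Table 9).** Replace the 11.2 sentence with: *Centre is a fixed or random effect; inference uses model-based standard errors with Satterthwaite or Kenward-Roger degrees of freedom; participant-clustered robust errors are a sensitivity analysis; no centre-clustered robust variance with a z reference is used.* If a centre-clustered variance is kept, refer it to t with centres minus 1 degrees of freedom.
- **Ordinal Global outcome (Table 9) and modified Poisson model (Table 11).** Keep a robust variance but cluster it on participant, with centre as a covariate. The modified Poisson model needs a robust variance because the outcome is binary, and the degrees-of-freedom methods above do not carry over to the ordinal model.

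This does not settle whether the healthcare-professional random effect in Protocol 10.2 belongs in the primary model. That needs its own decision.

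Cost: SAP wording and a software option, no new data, and slightly wider intervals. The fallback to t with centres minus 1 degrees of freedom costs more when centres are few (Step 4), which is a reason to prefer the model-based route.
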